METHODOLOGY: The specific aims are to: **(Aim 1)** Determine MR effectiveness for physical (pain, sleep), PTSD (intrusion, arousal, avoidance, numbing), and psychological (depression, stress, anxiety) symptoms, and global health (quality of life); **(Aim 2)** Determine MR effectiveness for social (relationship satisfaction, compassion for self/others) outcomes among Veterans and their partners; and **(Aim 3)** Describe Veteran and partner perceived value of MR in a sub-sample of participants. The sample will consist of Veteran and partner dyads (N = 600). **Aim 1 & 2** data collection will include self-report assessment of 4-data points over a 4-month period to evaluate physical, psychological, and social outcomes. Eight weekly reports will also be collected for the first two months of MR use to assess MR utilization, and pain and stress levels. **Aim 3** data collection will include telephone interviews from a selected sub-sample of 84 individuals to examine MR user experiences, study experiences, and to collect their suggestions for making MR useful for Veterans and their partners.

CLINICAL RELEVANCE: In a community-based trial in a non-clinically defined sample of Veterans, MR was associated with significant reductions in pain and PTSD-related symptoms. In the proposed study we will test MR's effects in a clinically defined population as a complement to clinical services. This program evaluation is needed to determine MR's appropriateness for implementation within the VA for clinically defined populations.

Aim 1: Determine MR effectiveness for physical (pain, sleep), PTSD (intrusion, arousal, avoidance, numbing), and psychological symptoms (depression, stress, anxiety), and global health (quality of life).

H1.1. Veterans who use MR will report significantly greater improvement in physical pain compared to those in the control group. (Primary Outcome)

H1.2. Veterans who use MR will report significantly greater improvement in PTSD and psychological symptoms, sleep and quality of life compared to those in the control group. (Secondary Outcomes)

Aim 2: Determine MR effectiveness for social (relationship satisfaction, compassion for self/others) outcomes among Veterans and their partners.

H2.1. Veterans and partners who use MR will report significantly greater improvement in social outcomes compared to the control group. (Secondary Outcomes)

Aim 3: Describe Veteran and partner perceived value of MR in a sub-sample of participants.

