Aim 1 & 2 assessment data will be collected from 600 Veteran/partner dyads (up to 200 per site, 100 dyads per arm) via a secure project website at baseline, 1, 2, and 4 months to assess primary and secondary outcomes. MR utilization and pain ratings will be assessed weekly for the first eight weeks of the intervention. This data collection plan will allow assessment of acute changes, rate of change with repeated measures over two months and sustained changes.

In **Aim 3**, a sub-sample of 84 individuals assigned to the intervention arm (n= 84 individuals, approximately 28 individuals/site) will be purposively selected (e.g., high or low MR utilization groups) to participate in telephone interviews to evaluate their experiences using the program. All consenting participants will be randomly assigned in a 1:1 ratio *using a permuted variable block design* to one of two arms (treatment vs. control). Participants will receive study information, instructions on how to complete the online data collection, and contact information in case they experience an adverse event. Participants will provide preferred contact information for data collection reminders. We will have contact information for each participant's primary care provider to ensure contact in the case of an adverse event and follow our established protocol for such events.

Treatment Arm: MR is a user-driven, dyadic, self-care management program developed with NIMH funding (R43/44) for use by Veterans and their selected partners, individually or together, to reduce pain and distress and support physical, mental, and relationship health. MR was designed for Veterans who face obstacles accessing formal mental health services. It can also be used to complement formal services. MR is a patient-centered intervention, allowing users to determine the pace at which to proceed in each program component.

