Sample Size Power Analysis: Aim 1&2, H1.1-H1.2 & H2.1 estimates of statistical power are based on Aim 1 and initially the primary outcome of pain. Whereas dyad is the unit of randomization, we assess power based on separate analyses for Veterans and partners (one approach used). There are 4 major intervals of assessment (baseline, 1, 2, and 4-months). At the beginning of this study, we estimated attrition based off of a previous MR trial that had less than 5% attrition. Based on early recruitment at the primary site, we have adjusted recruitment goals to allow for approximately 33% attrition, and uneven recruitment across the three study sites. Assuming within-subject (outcome measurement) correlation of 0.5, the proposed sample size will provide 80% power (2-sided type I error rate of 0.05) to detect a “small-to-medium” effect size of 0.38 (Cohen’s d). For analyses stratified by site (in addition to evaluation by random effect assessment), the study will provide 80% power to detect a “medium-to-large” effect size of 0.66. By way of comparison, the pilot data presented above describes large effect sizes ($d = 0.81$ for pain symptom reduction). While this effect size was based on a relatively small sample of comparable patients ($n < 15$) and within-subject assessment (paired t -test), it provides good assurance that the proposed sample size is sufficient to detect realistic, medium size effects should they exist with the MR program. For secondary outcomes, we will use a type I error rate of 0.01 for multiple comparisons. For the sample and our described assumptions, this will provide 80% power to detect a “medium” effect size of 0.45.⁵⁹

Sample Size: Qualitative- Aim 3 sample size relies on the quality and richness of information obtained.⁶⁰ Conceptual saturation is the goal of qualitative research, and depends on data to support interpretations. Saturation has been noted to occur within the first 12 interviews.^{60,61} Our team has extensive experience in evaluating electronic technologies, and have found recruiting high and low volume users provides the richest dataset. To ensure representative data, we will conduct telephone interviews with a purposive (e.g., high or low MR utilization group) sub-sample of up to 84 individuals to achieve representation at each site (approximately 28 individuals/site).

Data Collection Procedures. Data will be collected using (1) self-report surveys; and (2) telephone interviews.

(1) Self-reported Survey Data.

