Hypotheses Aims 1 & 2. All outcome measures (*primary and secondary*) under Aim 1 will be collected at baseline, 1, 2, and 4 months and are continuous variables. Therefore, general linear mixed models will be used with main effects terms for GROUP (MR vs. waitlist) and TIME (4-time points) and a GROUP x TIME interaction term (for rate of change). The models will also include site as a random effect. To assess whether the rate of change is curvilinear (i.e., the rate of change differs between time points), a quadratic parameter will be tested. Different correlation structures and functional forms of the effects of the MR program will be assessed using the information criteria and a final parsimonious model will be determined for final statistical inference. Initial effects of the MR program (baseline to 1-month) will be evaluated by analysis of covariance (ANCOVA). For H1.1, the primary outcome measure for pain will be total score on the 19-item POQ. For H1.2., the primary outcome measure for PTSD will be total score on the 20-item PCL-5. Subgroup analyses will be explored using similar methods and examination of severity of baseline pain and PTSD scores. These analyses will provide insight into subgroups in whom the MR program may be particularly beneficial. In a similar realm, analyses will be stratified by baseline median level of relationship satisfaction, as derived from total score on the 14-item RDAS. This will permit assessment of the effect of the MR intervention on potential improvement in relationship satisfaction among a cohort of dyads with presumably troubled relationships at entry. Moreover, using the weekly reports (8 weeks) of MR use and satisfaction with the MR program, the MR sample will be split above versus below the median for these two measures, and compared separately against the waitlist control condition at 2-months. This approach approximates a “per protocol” analysis in terms of recommended use of the MR program. In addition, especially for Aim 2 outcomes, we seek to examine whether dyads appear to show mutual benefits from the MR program. Therefore, multilevel models will be fit using an over-time dyadic model⁷⁸ in which individuals are nested within dyads and time is crossed with dyads (i.e., both Veteran and partner are assessed at the 4 time points). This analysis accounts for the non-independence due to the correlation between dyad members’ general levels on outcomes averaged over time, as well as the time-specific correlation between their outcomes (e.g., similarity caused by time-specific events).

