69. Beck, A. T., Steer, R. A., Ball, R. & Ranieri, W. F. Comparison of Beck Depression Inventories-IA and-II in Psychiatric Outpatients. *J. Pers. Assess.* **67**, 588–597 (1996).

71. Buysse, D. J., Reynolds, C. F., 3rd, Monk, T. H., Berman, S. R. & Kupfer, D. J. The Pittsburgh Sleep Quality Index: a new instrument for psychiatric practice and research. *Psychiatry Res.* **28**, 193–213 (1989).

72. Busby, D. M., Christensen, C., Crane, D. R. & Larson, J. H. A Revision of the Dyadic Adjustment Scale for Use with Distressed and Nondistressed Couples: Construct Hierarchy and Multidimensional Scales. *J. Marital Fam. Ther.* **21**, 289–308 (1995).

73. NEFF, K. D. The Development and Validation of a Scale to Measure Self-Compassion. *Self Identity* **2**, 223–250 (2003).

74. Sprecher, S. & Fehr, B. Compassionate love for close others and humanity. *J. Soc. Pers. Relatsh.* **22**, 629–651 (2005).

75. Ten Have, T. R. *et al.* Intent-to-Treat vs. Non-Intent-to-Treat Analyses under Treatment Non-Adherence in Mental Health Randomized Trials. *Psychiatr. Ann.* **38**, 772–783 (2008).

77. ATLAS.ti: The Qualitative Data Analysis Software. Available at: <http://www.atlasti.com/>. (Accessed: 7th April 2011)

78. Statistical Analysis Software, SAS/STAT | SAS. Available at: <http://www.sas.com/technologies/analytics/statistics/stat/index.html>. (Accessed: 7th April 2011)

Updated Statistical Analysis Plan

Under Aim 1, data for PRO (Patient Reported Outcomes) will be collected at Baseline, Weeks 1, 2, 3, 4, 5, 6, 7, 8, and 16. Pain, Stress, and Tension will be collected as a single-item scale measures, alongside intervention utilization, intervention satisfaction, and waitlist control pain/PTSD symptom mitigation activities weekly. All other PROs will be collected at Weeks 4 (Month 1), 8 (Month 2), and 16 (Month 4) (*see Table 1: Veteran and Partner Measures and Psychometric Properties in Protocol for further details*). General linear mixed models will be used with main effects terms for GROUP (MR vs. waitlist-control), TIME (continuous time measure from days from activation in protocol) and a GROUP x TIME interaction term (for rate of change).

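### The effects printed at 80% power (0.38, 0.66 and 0.45) do not follow from 600 dyads with 33% attrition: they are conservative at that enrolment, and the N and test behind them are not stated

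*Combined protocol and SAP*

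**What the plan says.** Enrolment is given as 600 dyads in the Methodology summary ("The sample will consist of Veteran and partner dyads (N = 600") and in Study Design and Overview ("collected from 600 Veteran/partner dyads (up to 200 per site, 100 dyads per arm"). The section on Human Subjects Involvement and Characteristics repeats the total and the cap per site.

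The Sample Size Power Analysis bases power on separate analyses of Veterans and partners, with four assessments and a within-subject correlation of 0.5. On attrition it says "we have adjusted recruitment goals to allow for approximately 33% attrition, and uneven recruitment across the three study sites". It then gives three effects:

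- Overall, "the proposed sample size will provide 80% power (2-sided type I error rate of 0.05": d = 0.38.
- By site, "For analyses stratified by site (in addition to evaluation by random effect assessment), the study will provide 80% power to detect": d = 0.66.
- Secondary outcomes at alpha 0.01, "For the sample and our described assumptions, this will provide 80% power": d = 0.45.

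No test is named for these figures. Data Analysis plans a mixed model with "main effects terms for GROUP (MR vs. waitlist) and TIME (4-time points) and a GROUP x TIME interaction term". The Updated Statistical Analysis Plan changes time to "TIME (continuous time measure from days from activation in protocol) and a GROUP x TIME interaction term (for rate of change" and does not revisit power.

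**The concern.** A detectable effect is tied to an analysed N, a test and an assumed pattern of effect. Here the only N on offer is 600 dyads, and the printed effects look too large for it. If so, a reader cannot say what effect the trial was sized to detect or at what enrolment. That matters when a null result is interpreted, or when someone must decide whether enrolment below the ceiling is enough. In both cases the printed effects would be the benchmark.

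**Working it through.** **Inputs from the documents.** Enrolment is 600 dyads, up to 200 per site, allocated 1:1. Attrition is 33%, r = 0.5, and visits are at months 0, 1, 2 and 4. Two-sided alpha is 0.05. For secondary outcomes alpha is 0.01, taken as two-sided. Each analysis uses one person per dyad, so there is no within-dyad design effect.

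**Assumptions.** Completers only; equal correlation between all visits; d is the month-4 group difference in single-visit SD units; no variation of the effect between sites. Six time patterns of the effect (months 0, 1, 2, 4) are tried: (0,1,1,1), (0,.25,.5,1), (0,1/3,2/3,1), (0,.5,.5,1), (0,.5,1,1), (0,0,0,1).

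**Step 1: can the printed figures be reproduced at all?** Choose n so that 80% power falls at d = 0.38. Then compute the effect at alpha 0.01 and the effect at one third of that n.

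| Test | Enrolled N giving 0.38 | At alpha 0.01 (printed 0.45) | By site (printed 0.66) |
|---|---|---|---|
| GROUP x TIME, 4 points (3 df) | 302-453 | 0.453 | 0.661-0.663 |
| Continuous-time slope (1 df) | 281-465 | 0.464 | 0.658 |
| Two-group change score | 328 | 0.465 | 0.664 |

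The 3-df test matches all three printed values under every pattern. If 0.38 is a rounding of anything from 0.375 to 0.385, the other two tests still give at least 0.457 at alpha 0.01, which does not round to 0.45.

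**Step 2: analysed numbers at 600.** 600 x 0.67 = 402, or 201 per arm. A full site has 200 x 0.67 / 2 = 67 per arm.

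**Step 3: detectable effects at those numbers.**

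*3-df test.* The noncentrality is (n/2) d² Q, where Q is the sum of squared deviations of the pattern from its mean, divided by (1 - r). Q runs from 1.0 to 1.5 over the six patterns. For 80% power the noncentrality must be 10.94 at alpha 0.05 (11.01 at site level) and 15.53 at alpha 0.01. So d = sqrt(2 x noncentrality / (nQ)):

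- Overall: sqrt(21.88/301.5) = 0.27 to sqrt(21.88/201) = 0.33.
- By site: sqrt(22.02/100.5) = 0.47 to sqrt(22.02/67) = 0.57.
- Alpha 0.01: sqrt(31.06/301.5) = 0.32 to sqrt(31.06/201) = 0.39.

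*Slope.* The sum of squared deviations of 0, 1, 2, 4 is 8.75, so a person's slope has variance 0.5/8.75 = 0.0571. The patterns imply a slope b of 0.200 to 0.257 per unit of d. So d = (z for alpha + z for power) x sqrt(2 x 0.0571/n) / b. For example, overall: 2.802 x 0.02385 = 0.0668; 0.0668/0.257 = 0.26 and 0.0668/0.200 = 0.33.

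*Two-group change score.* At r = 0.5 its variance, 2(1 - r), is 1. So d = 2.802 x sqrt(2/201) = 0.28, and the noncentral t gives 0.280.

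| Test at 600 dyads | Overall (printed 0.38) | By site (0.66) | Alpha 0.01 (0.45) | Power at printed effects |
|---|---|---|---|---|
| 3-df | 0.27-0.33 | 0.47-0.57 | 0.32-0.39 | 91-99% |
| Slope | 0.26-0.33 | 0.45-0.58 | 0.32-0.41 | 88-99% |
| Two-group | 0.28 | 0.49 | 0.34 | about 97% |

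**Step 4: the other reading of 33%.** Human Subjects Involvement and Characteristics describes the 33% as over-sampling. Then 600/1.33 = 451 complete, and the 3-df test detects 0.25-0.31 overall. This is further from the printed value.

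**The case against.** The best defence is that nothing is wrong. The site figure is a cap, and goals were raised for attrition and for uneven sites, so the authors may have kept effects that belong to a smaller expected N. The wording allows this, and Step 1 shows that the three figures belong together. But that N appears nowhere, and the paragraph attributes the effects to the proposed sample size.

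It is also fair to say that the test is partly inferable. The paragraph mentions four assessments, a within-subject correlation and random effects, and the figures fit the 3-df interaction. That stands as inference. The test is still unnamed, the SAP later makes time continuous, and even under the 3-df test the N depends on the pattern.

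Finally, 402 counts completers. The plan analyses by intention to treat, adds imputation, and uses a mixed model that can draw on partial follow-up. This too is right, but any extra information would lower the detectable effects and widen the gap.

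Some stronger readings are tempting, and the documents do not support them:

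- *The trial is underpowered.* At 600 dyads the opposite holds.
- *The true target can be back-solved from 0.38.* It cannot without the effect pattern: 302-453 even with the test fixed.
- *The stated recruitment rate rules out 600.* Three to four dyads per month at three sites over all 48 months gives 432-576. But the bars of the GANTT chart are missing from the text available, and falling short of a ceiling is not a contradiction.
- *The 200 dyads in the Sample section contradict 600.* That sentence already refers to Tampa.

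**Conclusion.** The concern holds. None of the three printed effects follows from 600 dyads, 33% attrition and r = 0.5 under either planned form of the GROUP x TIME test or a simple two-group comparison. Under the four-time-point test the detectable effects are about 0.05-0.11 below the printed 0.38, 0.09-0.19 below 0.66 and 0.06-0.13 below 0.45.

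The error is conservative at 600 dyads, but that should not be carried to a lower enrolment. As an illustration only, 300 dyads (100.5 completers per arm) would give the two-group comparison about 76% power for 0.38 and 72% for 0.45 at alpha 0.01.

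The mismatch itself is certain under the stated inputs. The ranges rest on the six assumed patterns, equal correlations and completers only. That the figures came from a 3-df calculation at a smaller N is likely but remains an inference. This should be fixed, as a correction to the power statement and not to the trial.

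**What to change.** Keep the design, the enrolment and the tests. In the Sample Size Power Analysis:

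1. State the N to which the power refers, both enrolled and assumed to complete.
2. Name the planned mixed-model GROUP x TIME test, say whether time has four levels or is continuous, and give the assumed pattern of effect.
3. Restate the three detectable effects for those choices. At 600 dyads with four time points they fall within 0.27-0.33, 0.47-0.57 and 0.32-0.39; the chosen pattern fixes the value. The two-group figures are a check and should not be printed as the plan's, because that is not the planned test.
4. If the printed effects were meant for a lower expected N because of uneven sites, state that N instead.
5. Say whether 33% is attrition (about 402 completers) or over-sampling (about 451), and use the same term in Human Subjects Involvement and Characteristics.

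The cost is one recalculation and a rewording of the power paragraph, with a matching phrase in the human subjects section.

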Exclusion criteria will be: Moderate to severe TBI, diagnosis or documented treatment for psychosis in previous 6 months, currently in high-intensity substance use disorder treatment, non-English speaking; visual, hearing, cognitive impairment that prevent participation or ability to consent, self-report history of partner/family member physical abuse in the past year, and/or lack of access to internet service. These individuals will be excluded due to medical, language, and technology access issues that would prevent safe and full study participation. As stated above, *potential participants who screen for aggression or violence will also be excluded from study.*

Randomization: Participants (dyads) will be randomized to treatment (MR) or control using a per site variable block randomization method (blocks of 6 and 8) to facilitate a balance in treatment and control group sizes per site and over time. Variable blocks of 6 and 8 per site will be randomly used so that no one will know for sure the next random assignment. Dyad is the unit of randomization; this ensures that members of the same couple receive the same intervention. The randomization will be stratified by whether or not the veteran is currently receiving, or has received in the past 2 weeks, a Level 1 evidence-based treatment for pain and/or PTSD, per current VA-DoD treatment guidelines.

This will facilitate subgroup analyses of the effect of the MR intervention in the presence versus absence of concomitant first-line evidence-based treatment for pain and PTSD. A computer-generated random allocation sequence will be generated by the study biostatistician (separately for each site/era of service combination to ensure balance across sites, that is, control for site effects by design). [name] and [name] will be responsible for monitoring participant (dyad) assignment. Participant dyads randomized to the treatment group will receive a link, and PIN to access the MR site and will be instructed to create personal user accounts. Control group members will receive access to MR after completing data collection.

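### Subgroup analyses by median RDAS, baseline severity and concomitant treatment are planned without a treatment-by-subgroup interaction test

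*Combined protocol and SAP*

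**What the plan says.** Three sets of subgroup analyses are planned.

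- **Baseline severity** (protocol, Data Analysis, Hypotheses Aims 1 & 2): "Subgroup analyses will be explored using similar methods and examination of severity of baseline pain and PTSD scores". The purpose follows at once: "These analyses will provide insight into subgroups in whom the MR program may be particularly beneficial".
- **Relationship satisfaction** (same paragraph, introduced as being in the same vein): "analyses will be stratified by baseline median level of relationship satisfaction, as derived from total score on the 14-item RDAS". The stated purpose is to see the effect on relationship satisfaction in dyads presumed to be in difficulty at entry.
- **Concomitant treatment** (protocol, Randomization), given as a reason for stratifying the randomisation: "This will facilitate subgroup analyses of the effect of the MR intervention in the presence versus absence of concomitant first-line evidence-based treatment".

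The mixed model has GROUP, TIME and GROUP x TIME. The Updated Statistical Analysis Plan repeats those three terms and lists no subgroup analysis. Neither place gives a term for treatment by subgroup, a severity cut-point, a multiplicity rule for subgroups, or a criterion for saying that a subgroup benefits more. Table 1 collects the RDAS from Veterans and partners, but the plan does not say whose score sets the median.

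**The concern.** To say that a programme is particularly beneficial in some people is to compare effects between groups. GROUP x TIME asks whether the arms change at different rates overall; it says nothing about whether that difference varies with baseline RDAS, pain, PTSD or concomitant treatment. Analyses run separately in each half of a median split give two estimates and two p-values, but no test of the difference between them. One significant half and one non-significant half is a common chance result when the effect is identical in both.

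The median split has two further weaknesses. A sample median places about half the dyads in the low group whatever their actual scores, so it need not mark troubled relationships. It also discards information in a continuous score that the trial already collects.

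What is at stake is how the results are used. The Dissemination Plan (Table 2) foresees guidance on using MR in clinical care, and a chance contrast could influence who is offered it.

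**Working it through.** **Inputs from the protocol.** Sample Size Power Analysis: "effect size of 0.38" at 80% power and two-sided alpha 0.05; alpha 0.01 for secondary outcomes; about 33% attrition; a pilot d of 0.81. Study Design and Overview: 600 dyads, 1:1. The Sample paragraph gives 200 dyads at Tampa.

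**Assumptions.** Normal approximation with SD 1; two equal, independent halves; the same true d in both; and a rule that names a subgroup when it alone is significant. The plan does not state that rule.

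**1. The plan's own figure.**

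- n per arm = 2 × (1.960 + 0.842)² / 0.38² = 2 × 7.849 / 0.1444 = 108.7, so 109 per arm (218 analysed dyads).
- 600 less 33% = 402, or 201 per arm. The detectable effect is 2.802 × √(2/201) = 0.28.

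So 0.38 does not follow from 600 dyads less 33%. Both sizes are carried forward, with 200 less 33% = 134 (67 per arm) as a low case.

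**2. Power in one half when overall power is 80%.** The overall standardised effect is 1.960 + 0.842 = 2.802. Each half has half the participants, so 2.802 / √2 = 1.981, and power = Φ(1.981 − 1.960) = 0.508.

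P(exactly one half significant) = 2p(1 − p) = 2 × 0.508 × 0.492 = 0.50. This follows from 80% power alone, so the uncertain sample size does not affect it.

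**3. Other cases.** Power per half = Φ(d / √(2/m) − 1.960), with m per arm per half. Example, 402 dyads: m = 100.5, √(2/100.5) = 0.1411, 0.38 / 0.1411 = 2.694, Φ(0.734) = 0.768, and 2 × 0.768 × 0.232 = 0.356.

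| Analysed dyads (per arm) | True d, same in all | Power per half | Exactly one half significant |
|---|---|---|---|
| 218 (109) | 0.38 | 51% | 50% |
| 402 (201) | 0.28 | 51% | 50% |
| 402 (201) | 0.38 | 77% | 36% |
| 134 (67) | 0.38 | 34% | 45% |
| 218 (109) | 0.81 | 99% | 2% |
| 402 (201) | 0.81 | 100% | about 0% |
| 134 (67) | 0.81 | 91% | 16% |
| any | 0 | 5% | 9.5% |

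**4. At the secondary alpha.** Relationship satisfaction is a secondary outcome, and the protocol says: "For secondary outcomes, we will use a type I error rate of 0.01 for multiple comparisons". With 80% overall power at 0.01: (2.576 + 0.842) / √2 = 2.417; Φ(2.417 − 2.576) = 0.437; 2 × 0.437 × 0.563 = 0.49.

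**5. An interaction test instead.** With no true difference between subgroups, its false-positive rate is its alpha, 5% per factor at 0.05, whatever the overall effect. The cost is power. The SE of the difference between halves is √2 × √(2/m): 0.271 with 218 dyads and 0.1995 with 402.

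- Power for an interaction of 0.38: Φ(0.38/0.271 − 1.960) = 29%, and Φ(0.38/0.1995 − 1.960) = 48%.
- Interaction detectable with 80% power: 2.802 × 0.271 = 0.76, and 2.802 × 0.1995 = 0.56.

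**6. Several factors.** Four independent interaction tests at 0.05 give 1 − 0.95⁴ = 18.5%. In a simulation of three median-split factors (8,000 runs, d = 0.38, correlations of 0.3 to 0.5 between factors assumed), at least one one-sided contrast in significance appeared in 57% of trials with 402 dyads and 74% with 218. Interaction tests gave at least one false positive in 13% to 15%.

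**The case against.** A reader might infer that the plan fits separate models within severity strata and will often name a false subgroup. The documents do not support that.

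- Only the RDAS analysis is described as stratified. The severity analyses are to use similar methods, which could include a moderator term, and the concomitant-treatment analyses have no stated method.
- No rule for naming a subgroup appears. Comparing significance across halves is an assumption of the calculation, the severity wording is exploratory, and none of the hypotheses concerns a subgroup.
- The RDAS sentence has its own aim, the effect among dyads presumed troubled. Estimating an effect in one stratum does not require a contrast between strata.
- The rate depends on the true effect. At the pilot's d = 0.81 it almost vanishes with the larger samples.
- The Updated Statistical Analysis Plan omits subgroups, so they may no longer be intended.

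Most of this stands and limits the claim to a conditional one. It does not remove the gap. The severity analyses have a comparative purpose and no comparative test. The RDAS analysis is presented as similar in kind, and its median is a weak marker of difficulty even for an effect within one stratum. The pilot figure is, by the protocol's own account, a within-subject result from fewer than 15 patients. The SAP's silence is a reason to ask, not evidence of withdrawal.

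**Conclusion.** The point holds in a limited form. The plan stratifies at the median RDAS and foresees severity and concomitant-treatment subgroups, but names no test of whether the MR effect differs between them.

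If significance in the two halves is compared, an identical effect in everyone produces a one-sided contrast in about 50% of trials at 80% overall power (about 49% at alpha 0.01). It is 36% at d = 0.38 with 201 analysed per arm, 9.5% with no effect, and about 0 to 2% at d = 0.81 with 109 or more per arm. The comparable error of an interaction test is 5% per factor.

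These figures rest on the assumed rule, equal halves and a normal approximation. The 109 and 201 per arm are derived here, not stated in the plan. The primary hypothesis test is unaffected.

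**What to change.** Amend the SAP as follows.

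1. State that the subgroup analyses remain and are exploratory, and list the factors.
2. Replace the median split with one model on all randomised dyads that tests GROUP by continuous baseline score (RDAS, POQ, PCL-5) and GROUP by the concomitant-treatment randomisation stratum.
3. Where the moderator is the baseline of the outcome being analysed, model only the follow-up scores, with baseline as a covariate and in the GROUP interaction. Baseline is one of the four response times in the protocol's model, so the same score would otherwise stand on both sides. Where baseline stays as a response, the moderator must multiply GROUP x TIME, because that term carries the treatment effect.
4. Say whose RDAS is used: Veteran, partner or dyad mean.
5. Report each interaction estimate with its interval, and the MR effect at scores chosen in advance. A low RDAS value among them answers the question about troubled relationships directly.
6. Make no subgroup claim from p-values within strata.

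The cost is SAP text and some model terms, with no new data. The intervals will be wide, with power of only about 29% to 48% for an interaction of 0.38 with 218 to 402 analysed dyads. Several interaction tests also raise the overall false-positive rate (18.5% for four independent tests at 0.05), which is a further reason for the exploratory label.
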